Title: The effect of lumbar stabilization and walking exercises on chronic low back pain: A randomized controlled trial

NCT number : NCT02938169

Date of document: April, 2017

Materials and Method

This study was a prospective randomized controlled clinical trial with four groups: flexibility exercise (FE) group, walking exercise (WE) group, stabilization exercise (SE) group, and stabilization with walking exercise (SWE) group. Subjects in this study were part of a clinical trial (NCT02938169). The study and all procedures were approved by the Institutional Review Board of Seoul National University Bundang Hospital (B-1604-344- 004).

Subjects This study was conducted between May of 2016 and April of 2017. Patients complaining of chronic LBP were recruited from the rehabilitation outpatient clinic. The inclusion criteria were subjects aged over 20 years with intermittent chronic low back pain of more than 3 months. The exclusion criteria were as follows: a pain intensity of below VAS 40 sease, severe knee or hip arthritis that may interfere with walking exercise, pregnancy, and previous exercise treatment for lumbar paraspinalis muscles within 3 months. The physical examination was done by a PMR specialist.

Sample Size Calculation One way ANOVA power analysis was performed with the help of a statistical team to compare the average values of the four groups. As a result, the power of 82% was obtained when 10 patients were allocated to each group. As a result, 15 patients were assigned to each group to account for a dropout rate of 30%.

Randomization Consenting participants were randomly allocated to one of four study groups, following the predetermined and computer-generated random allocation sequences that were prepared by a statistician not involved in participant recruitment. The randomization schedule was only accessible by two individuals: the statistician and the primary investigators.

Blinding It was not possible to blind participants and physiotherapists given the nature of the exercise therapy and evaluation. One researcher blinded to group allocation measured the outcomes at pre-, immediately post-, and 6 weeks post-exercise program. Statisticians and primary investigators were unaware of the group allocation until data analyses were complete.

Exercise protocol Participants underwent each exercise for 30~60 minutes, 5 times a week, for a

total duration of 6 weeks. All participants were educated on the correct posture and abdominal bracing method, and received a pamphlet explaining good postures and abdominal bracing method for preventing LBP. Light abdominal bracing exercise (10-20% of maximal bracing) was recommended for all times; maximal bracing was recommended for 5-7 seconds, intermittently. The education session was performed at the clinic by a trained physical therapist at the first visit. Moreover, a printed pamphlet with instructions on how to perform the exercises was given to each patient. The exercises were performed at home. All participants underwent a telephone interview every two weeks to confirm the current pain status, degree of exercise compliance, and to adjust the exercise level. Telephone communication also acted as an encouragement to exercise, promoting compliance.

The FE group received stretching exercise for the abdominal muscle, quadriceps, hamstring, tensor fascia lata, piriformis muscle, and quadratus lumborum muscles for 30 minutes. The WE group performed fast walking on flat ground with abdominal bracing for 30 minutes. The SE group was educated on IGLSE, focusing on the modifiable intensity level based on the exercise capacities of each participant. The IGLSE protocol consisted of two parts: stretching exercises and stabilization exercises. All participants performed stretching exercises for 5 minutes as a warm-up before beginning the stabilization exercises for 25 minutes. This program ranged from easy to difficult, based on participants' exercise capacity. Each exercise level had seven basic positions: supine, dead bug, side lying, prone, bird dog, bridge, and plank (five levels). We gradually increased the degree of instability until the most unstable posture was achieved. At the beginning, participants were placed into a level with moderate difficulty. To challenge the stabilization of all trunk muscles (anterior, lateral, and posterior), including the transverse abdominis, rectus abdominis, erector spinae and multifidus, internal oblique abdominals, and quadrates lumborum, participants were instructed to complete all five exercise positions in each session. Patients repeated each of the 7 postures 5 times for about 30 seconds each, to the best of their ability, for a total of 25 minutes.^{12, 13} The SWE group performed IGES for 30 minutes and walking for an additional 30 minutes.

Outcome measurement The primary outcome was the changes of VAS of LBP from the baseline to the follow-up. VAS was measured during rest and physical activity. The secondary outcomes included VAS of radiating pain measured during rest and physical activity, frequency of medication use (number of taking medications / day), endurance of specific posture (squared posture), and strength of lumbar extensor muscles. Endurance was measured in three postures (supine, side-lying, and prone)¹². The strength of lumbar extensor was measured with the manual muscle

tester (FEI 12-0380 Lafayette® Manual Muscle Tester, Fabrication Enterprises Inc., USA) in sitting position. In addition, Oswestry disability index and Beck depression inventory were measured to identify kinesiophobia, psycho-social aspects, and the disability for low back pain.

The first follow-up evaluation was done within 2 weeks after the completion of the 6-week exercise program, and all the initial evaluations were rechecked (immediately post-exercise program). The second follow-up evaluation was performed 12 weeks after the start of the program (6 weeks post-exercise program). At this evaluation, frequency and duration of exercise, as well as VAS of back pain and radiating pain during rest and physical activity were rechecked via telephone questionnaire to investigate the long-term compliance and effectiveness of the exercise treatment. Participants were advised to continue the exercise routine for the full duration of the program and that the second follow-up evaluation would be performed at the 12-week.

Statistical Methods SPSS 21.0 software (SPSS Inc, Chicago, IL, USA) was used for all statistical analyses. Wilcoxon signed rank test was used to compare the variables before and after the exercise in each group. Kruskal-Wallis test was used to compare the four groups. Repeated measures ANOVA was used to compare the pain scores (VAS) at various time points: first week (pre-exercise program), sixth week (immediately post-exercise program), and twelfth week (6 weeks post-exercise program). The results are presented as the mean \pm standard deviation. P values of less than 0.05 were considered statistically significant.

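### Allocation concealment is not assured: the primary investigators have access to the predetermined schedule, no release procedure is described, and the access sentence conflicts with the statement that they were unaware of allocation

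*Combined protocol and SAP*

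**What the plan says.** All of the relevant text is in the Subjects, Randomization and Blinding sections of the combined protocol and SAP.

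- **Sequence.** Allocation used "predetermined and computer-generated random allocation sequences that were prepared by a statistician not involved in participant recruitment".
- **Access.** "The randomization schedule was only accessible by two individuals: the statistician and the primary investigators". No time limit is attached. The sentence counts two people but uses a plural for the investigators, so the number of list holders is also unclear.
- **Consent.** "Consenting participants were randomly allocated to one of four study groups", which puts consent before allocation.
- **Knowledge of allocation.** "Statisticians and primary investigators were unaware of the group allocation until data analyses were complete".
- **Assessment.** "One researcher blinded to group allocation measured the outcomes at pre-, immediately post-, and 6 weeks post-exercise program".
- **Entry criteria.** One exclusion is "severe knee or hip arthritis that may interfere with walking exercise"; another is pain below 40 on the VAS. Patients came from a rehabilitation outpatient clinic and were examined by a PMR specialist. Neither the recruiter nor the examiner is identified as being, or not being, a primary investigator.

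The document mentions no envelopes, no central or web release, and no order for eligibility, baseline VAS and assignment.

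**The concern.** Concealment means that whoever decides on entry cannot know the next arm. The plan separates the author of the sequence from recruitment but makes no such statement about the other holders of the list. If a list holder also screened or enrolled, that person could accept, defer or exclude a candidate in the knowledge of the next assignment.

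The entry criteria leave room for this. Whether arthritis is severe enough to interfere with walking is a judgement, and it bears directly on the two arms that walk. The pain threshold is self-rated on the same kind of scale as the primary outcome, change in VAS.

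At stake is whether the four groups are exchangeable at entry. A Kruskal-Wallis test cannot tell a treatment effect from an imbalance built in at enrolment. Blinding later in the trial, whether of the assessor or of the analysis file, acts after the selection has been made.

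**Working it through.** **1. The sentences side by side**

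| Question | What the document states | What it leaves open |
|---|---|---|
| Who made the sequence? | A statistician outside recruitment | Block size, stratification |
| Who can see it? | That statistician and the primary investigators | From when, until when, how many people |
| Who enrols? | Not stated | Whether a list holder enrols |
| How is an assignment released? | Not stated | Singly or as an open list |
| What comes before assignment? | Consent | Eligibility check, baseline VAS |
| Did the investigators know allocation? | No, until the analyses were complete | How this fits with access to the schedule |

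The second and last rows conflict. A person with the schedule is able to know allocations. The two statements fit together only under something the document does not say, for example that access was nominal and never used, or that the list was coded.

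**2. How much could selective enrolment matter?**

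The plan gives no figure for this. The arm size comes from the Sample Size Calculation section and reproduces: 10 / 0.70 = 14.3, rounded up to 15 per arm, and 4 × 15 = 60.

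Assumptions, none of them from the documents:
- There is no true difference between arms.
- A visible prognosis correlates ρ = 0.3 to 0.5 with VAS change.
- On *s* occasions, a candidate in the worst prognostic third is deferred when the next slot is in the favoured arm, and the next arrival takes the slot.

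For a standard normal prognosis the worst third lies below z = −0.431, and its mean is −φ(z)/(1/3) = −0.3636/0.3333 = −1.09. The replacement has mean 0. Each deferral therefore gains 1.09 SD of prognosis for one of 15 places:

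gap = ρ × *s* × 1.09 / 15 (in SD of the change score).

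- **One arm, two or three deferrals.** 0.3 × 2 × 1.09 / 15 = 0.044, up to 0.5 × 3 × 1.09 / 15 = 0.109.
- **Two arms steered in opposite directions, two or three deferrals each.** Double the above: 0.087 to 0.218.
- **Two arms steered at every opportunity.** About 15/3 = 5 deferrals per arm: 2 × 0.3 × 5 × 1.09 / 15 = 0.218, up to 2 × 0.5 × 5 × 1.09 / 15 = 0.363.

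Simulating the same mechanism with Kruskal-Wallis at 0.05 gives:

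| Steering | Gap (SD) | Type I error |
|---|---|---|
| One arm, 2 to 3 deferrals | about 0.04 to 0.1 | about 5% |
| Two arms, 2 to 3 deferrals each | about 0.09 to 0.21 | about 5% to 7% |
| Two arms, persistent | about 0.2 to 0.36 | about 6% to 11% |

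**The case against.** The case against has four parts.

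*The investigators are said to have been unaware of allocation.* Read literally, that denies the knowledge on which steering depends. It stands as a reason not to call concealment broken. It does not settle the matter, because it contradicts the access sentence and the document does not say which one governed.

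*There are safeguards.* Consent precedes allocation, and a blinded researcher took the pre-program measurements. Both deserve credit. The second limits biased scoring of baseline VAS. Neither stops someone with the list from choosing whom to approach, or when, because a predetermined list can be read before consent is sought.

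*The gap may be one of reporting.* That is possible. A garbled stretch of text sits in the exclusion criteria, but the Randomization and Blinding paragraphs read as complete, and the access rule is stated there outright.

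*The effect may be small.* This largely stands. A reader might infer that, with 15 per arm, two or three steered enrolments could manufacture a significant result. Exchanging the two or three worst-prognosis members of one completed arm with the best of another does give type I error of about 7% to 18%. That calculation needs every prognosis known at once and participants moved after assignment, which reading a list of upcoming assignments does not allow. Deferral, the mechanism at issue, gives near-nominal error for a few candidates in one arm.

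**Conclusion.** The point holds as a failure to assure concealment, joined to an internal contradiction. The primary investigators are given access to a fixed schedule; nothing separates them from enrolment; the release method, the enrolling role and the order of steps are missing; and the plan elsewhere says they did not know allocation.

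A reader might go further and infer that allocation was known during recruitment and that enrolment was steered. The documents do not support that: they give neither the timing of access nor the role of the primary investigators in screening.

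The size depends on assumed values of ρ and on how persistent any steering was. A few deferrals for one arm would do little; systematic steering of two arms could raise type I error to about 6% to 11%. The case for change rests on a cheap remedy for an avoidable risk, and on two sentences that cannot both stand unexplained. It should be addressed, with medium confidence.

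**What to change.** **In the protocol.** State that, until the last participant is enrolled, the schedule is held only by the statistician who is not involved in recruitment. Release each assignment singly, after consent, the eligibility checklist and baseline VAS have been recorded and dated. Then make the access sentence and the unawareness sentence agree.

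**If recruitment has already run under the stated rule.** This is probably the case: the document is dated April 2017, and the Subjects section describes a study conducted from May 2016 to April 2017. Report who held the list and when, who enrolled, how assignments were released, whether eligibility and baseline VAS came first, and baseline characteristics by arm. Do not claim concealed allocation unless the investigators had no access during enrolment.

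**Cost.** The prospective change takes a few sentences and one message to the statistician per enrolment, 60 in all, with a short wait for each assignment. No extra staff are needed, since the statistician already holds the list. The disclosure takes a short paragraph and a baseline table. Sample size and analysis are unchanged.

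### No VAS condition, visit or test is designated primary, and all tests share one unadjusted 0.05 threshold

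*Combined protocol and SAP*

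**What the plan says.** Outcome measurement defines the primary outcome in one sentence: "The primary outcome was the changes of VAS of LBP from the baseline to the follow-up". The next sentence gives two conditions: "VAS was measured during rest and physical activity".

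The same section then describes two follow-ups:
- "The first follow-up evaluation was done within 2 weeks after the completion of the 6-week exercise program", when all the initial evaluations were repeated;
- "The second follow-up evaluation was performed 12 weeks after the start of the program", when "VAS of back pain and radiating pain during rest and physical activity were rechecked via telephone questionnaire".

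Low back pain VAS is therefore available in both conditions at both follow-ups.

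Statistical Methods lists three procedures:
- within groups, a paired before-and-after comparison of each variable by the Wilcoxon signed rank method;
- between groups, stated in full as "Kruskal-Wallis test was used to compare the four groups";
- over time, an ANOVA with repeated measures of the VAS pain scores at weeks 1, 6 and 12.

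A single significance threshold of 0.05 closes the section. The document names no primary condition, visit or test, and gives no testing order, multiplicity adjustment or rule for calling the trial positive. It does not say which term of the repeated measures ANOVA (group, time or their interaction) is to be tested.

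**The concern.** A four-group trial needs one comparison, fixed in advance, that decides its main question. Here the primary outcome sentence fits several comparisons, each with its own P value and each judged at 0.05. The one that decides the trial could be chosen once the P values are known.

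The masking described under Blinding does not prevent this. A four-group P value can be read without knowing which code belongs to which exercise program, so a favorable condition or visit can be picked while the codes are still masked.

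There is a second exposure. The Wilcoxon tests do not compare groups. A plan that does not rank them below the between-group test leaves room for a within-group result to be presented as the trial's finding.

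**Working it through.** The plan states no error rate for its primary outcome, so there is no figure to reproduce. The check counts the eligible comparisons and then sizes the consequence.

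**1. Count of between-group tests.** Conditions: 2. Follow-ups: 2. Three readings fit the text:
- A: Kruskal-Wallis on every VAS change, 2 × 2 = 4 tests.
- B: Kruskal-Wallis on the post-program changes only, 2 × 1 = 2 tests.
- C: repeated measures ANOVA as the VAS analysis, one model per condition, 2 tests. This compares groups only if group-by-time is the term tested.

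**2. Reference under independence.** Rate = 1 − (1 − 0.05)^k.
- k = 2: 1 − 0.95² = 9.75%.
- k = 4: 1 − 0.95⁴ = 18.5%.

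These overstate the rate, because the tests share patients and baselines. The Kruskal-Wallis test is also slightly conservative at this size (about 4.5% for a single test).

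**3. Simulation with correlation.** From the document: 4 groups; 10 per group as the powered number and 15 as the number assigned; threshold 0.05. Assumed, because the document gives none: normal VAS scores, all correlations, no true effect, and any one significant between-group result counting as positive. Change = follow-up minus the same baseline. Kruskal-Wallis rows used 40,000 trials per setting; repeated measures rows used 20,000.

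| Reading, 10 per group | Correlation over time | Rest–activity correlation 0 | 0.5 | 0.9 |
|---|---|---|---|---|
| A, four Kruskal-Wallis | 0.5 throughout | 15.9% | 15.1% | 12.2% |
| A, four Kruskal-Wallis | 0.7 between follow-ups, 0.3 with baseline | 14.1% | 13.5% | 10.9% |
| B, two Kruskal-Wallis | 0.5 throughout | 8.7% | 8.3% | 6.7% |
| B, two Kruskal-Wallis | 0.7 / 0.3 | 8.6% | 8.4% | 6.7% |
| C, two group-by-time tests | 0.5 throughout | 9.8% | 9.4% | 7.4% |
| C, two group-by-time tests, uncorrected | 0.7 / 0.3 | 12.9% | 11.6% | 9.1% |

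Reading C is worse under the 0.7/0.3 pattern because sphericity fails. With unit variances, the variance of a difference between two time points is 2(1 − ρ). That is 1.4 for each follow-up against baseline but 0.6 between the follow-ups.

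At 15 per group, reading A gives 16.6%, 15.5% and 12.9% with correlation 0.5 throughout (rest–activity 0, 0.5, 0.9), and about 11–15% under 0.7/0.3. Reading B gives 9.3%, 8.6% and 6.9% with correlation 0.5 throughout.

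**4. Within-group tests, kept separate.** Suppose all four groups improve by the same true amount, with 10 per group, one VAS change and an exact two-sided Wilcoxon test in each group. The share of trials in which some groups reach 0.05 and others do not is about 43% at a true change of 0.3 SD of the change score, 73% at 0.5 SD, 87% near 0.7 SD (the peak), 85% at 0.8 SD and 62% at 1.0 SD. This shows how often a tempting misreading would be available. It is not an error rate of the plan.

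**The case against.** The strongest reply is that one comparison was probably intended. The primary outcome sentence uses the singular for the follow-up, and the sample size rests on a single one-way ANOVA of four group averages. Repeated measures ANOVA is also the only procedure tied by name to VAS. Since it takes all three time points in one model, it could be the primary analysis, which would remove multiplicity across visits.

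Much of this stands. The repeated measures reading is natural and is counted above on equal terms. It does not close the gap: the plan does not call that test primary, does not name the term tested, and leaves two conditions. A singular follow-up does not say which visit is meant. The sample size paragraph names no VAS condition or visit, and its one-way ANOVA does not appear in Statistical Methods.

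Three stronger inferences are not supported:
- A reader might take 11–16% as the trial's false-positive rate. It needs both the widest reading and an any-significant-result rule, and the document states neither.
- A reader might treat the Wilcoxon percentages as an error rate of the plan. The plan lists a separate test to compare the four groups and nowhere says that a within-group result supports a between-group claim.
- A reader might infer that the primary comparison was in fact chosen after the results. Nothing in the document shows this; it shows only that the choice was left open.

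**Conclusion.** The point holds. The primary comparison is undefined in condition, visit and test, and that rests on the text alone, without any assumed correlation. It must be fixed because it concerns the trial's main conclusion.

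The size is conditional. It assumes no true effect, any one significant between-group result counted as positive, and the correlations shown. At 10 per group the false-positive rate is then about 7–9% for two Kruskal-Wallis tests and 11–16% for four. For two group-by-time tests it is 7–10% when sphericity holds. Uncorrected under the 0.7/0.3 pattern it is 9–12% for rest–activity correlations of 0.9 to 0.5, and near 13% at zero. At 15 per group the four-test figure is about 11–17%. Every reading exceeds 5%; on the narrower ones the excess is modest.

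The missing inputs behind the stated 82% power are a separate matter and form no part of this conclusion.

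**What to change.** Before any between-group test is run:
- Name one VAS condition, one visit (or one group-by-time term across visits) and one between-group test as the single primary comparison at 0.05. The choice is the sponsor's. If the repeated measures model is chosen, state the term tested and how non-sphericity is handled.
- Make the other between-group VAS comparisons secondary, in a fixed order or with Holm adjustment.
- State that the within-group Wilcoxon tests are descriptive and cannot support the between-group conclusion.

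The document is dated April 2017, the last month of the study period it gives, so tests may already have been run. In that case, report every between-group VAS comparison that was performed, with Holm over that family (two or four tests, according to the analysis actually used). Disclose that the choice was made afterwards.

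The cost is a few sentences and no patients. Measures not chosen lose primary status. If several are kept with Holm, power per measure is lower: the first Holm threshold is 0.05/2 = 0.025 for two tests and 0.05/4 = 0.0125 for four. As an illustration, take the effect that gives a one-way ANOVA 82% power with 10 per group at an assumed alpha of 0.05 (back-solved Cohen's f = 0.564). Power at those thresholds would be 72.7% and 62.6%.

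### The global Kruskal-Wallis test is followed by no pairwise contrast, no between-arm difference with a confidence interval and no multiplicity rule, and the only clearly arm-specific P values are before-after tests

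*Combined protocol and SAP*

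**What the plan says.** The Statistical Methods section names three procedures:

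- Within arms: "Wilcoxon signed rank test was used to compare the variables before and after the exercise in each group".
- Between arms: "Kruskal-Wallis test was used to compare the four groups".
- Over time: "Repeated measures ANOVA was used to compare the pain scores (VAS) at various time points". The text does not say whether this model has a group factor or is run arm by arm.

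On presentation it says "The results are presented as the mean", with the standard deviation. One threshold, P below 0.05, covers every test. No post hoc procedure, reference arm, priority contrast, between-arm estimate, confidence interval or multiplicity adjustment appears there or elsewhere in the document.

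The Sample Size Calculation section is also global: "One way ANOVA power analysis was performed with the help of a statistical team to compare the average values of the four groups". It gives no effect size or SD.

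**The concern.** The title asks about the effect of stabilization and walking exercise, and the four arms are flexibility (FE), walking (WE), stabilization (SE) and the combination (SWE). The natural questions are which programme does better and what combining adds. A significant Kruskal-Wallis test says only that the arms are not all alike. To go further with a P value, a reader of this plan has only the four before-after tests. Those measure change from baseline in one arm at a time and do not use the randomization. If every arm improves a good deal, all four tend to be significant even when one arm is truly better.

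If pairwise tests are added later without a stated rule, the choice of method is the analyst's. Six unadjusted pairs at 0.05 carry a family-wise error of about 20%.

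**Working it through.** **Inputs.** Four arms, 82% power at 10 per arm, 30% dropout and 15 assigned per arm (Sample Size Calculation); significance at P below 0.05 (Statistical Methods). Assumed, because the document gives no SD or expected change: two-sided tests, normally distributed changes with equal SD, and Kruskal-Wallis applied to changes. Differences are in units of the SD of change.

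**The plan's own figures.** Dropout: 10/(1 − 0.30) = 14.3, rounded up to 15, which reproduces. The power statement, "As a result, the power of 82% was obtained when 10 patients were allocated to each group", cannot be reproduced without an effect size, so I solved backwards. One-way ANOVA power is P[F′(3, 36; λ) > F₀.₉₅(3, 36)] with λ = 40f². Setting this to 0.82 gives f = 0.564. The same f at 15 per arm gives 95.7%.

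**What that f means between two arms.** The largest pairwise difference depends on the pattern of means:

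- Two arms against two: δ = 2f = 1.13 SD.
- One arm against three equal arms: f = δ√3/4, so δ = 4 × 0.564/√3 = 1.30 SD.
- Two extremes with two midway: δ = f√8 = 1.60 SD.

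I carry the middle case forward.

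**Can the planned tests pick out the better arm?** Simulation, one arm better by 1.30 SD, exact Wilcoxon tests, Kruskal-Wallis by chi-square. Kruskal-Wallis is significant in 77% of trials (n=10) and 94% (n=15). Among those trials:

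| Change in the other three arms | 0.5 SD | 0.8 SD | 1.0 SD | 1.5 SD |
|---|---|---|---|---|
| Only the better arm significant by Wilcoxon, n=10 | 39% | 7% | 1% | 0% |
| Same, n=15 | 20% | 1% | 0% | 0% |
| All four arms significant by Wilcoxon, n=10 | 1% | 18% | 44% | 94% |
| Same, n=15 | 6% | 50% | 82% | 99.8% |

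**Tukey contrasts in the same trials, on a matched criterion.** The better arm is separated from all three others, with no false pair, in about 45% (n=10) and 68% (n=15). These figures do not depend on the common change. On a looser criterion, at least one true pair and no false pair, they are 94% and 96%. Only the 45% and 68% are comparable with the Wilcoxon rows.

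**Power and precision of one Tukey contrast.** The critical value is 2.69 (36 df) or 2.65 (56 df).

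- Half-width of the simultaneous 95% interval: 2.69 × √(2/10) = 1.20 SD; 2.65 × √(2/15) = 0.97 SD. Unadjusted: 0.91 and 0.73 SD.
- Power at 1.30 SD: noncentrality 1.30 × √(10/2) = 2.91 gives about 59%; 1.30 × √(15/2) = 3.57 gives about 82%.

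**The case against.** The strongest defence is that the document is internally consistent. It powers a four-group comparison and tests four groups, Kruskal-Wallis is a valid randomized comparison, and no reference arm or pairwise objective is claimed. That stands, and it is why the global test should be kept. It does not supply the inference a reader needs once the test is significant.

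Three stronger readings are tempting, and the document does not support them.

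- A reader might infer that nothing would indicate the direction or size of a difference. That goes too far. If arm means of change are shown or can be derived, subtracting them gives a point difference. In the one-against-three case, after a significant Kruskal-Wallis test, the arm with the largest mean change is the truly better one in 99.8% of trials at n=10 and over 99.9% at n=15. What is missing is formal inference and precision.
- A reader might infer that the trial will rank arms by their before-after P values. No such rule is stated. With equal improvement in all arms, the Wilcoxon results would disagree between arms by chance in 62% to 85% of trials at n=10 for changes of 0.5, 0.8 or 1.0 SD, but in only 0.1% at 2.0 SD. This is a possible misreading, not a planned analysis, and Kruskal-Wallis rejects in under 5% of those trials.
- A reader might set the 94% and 96% for Tukey against the 39% for Wilcoxon. The criteria differ. Matched, the closest comparison at n=10 is 45% against 39%.

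The repeated measures ANOVA might include group. The text does not say so. With a group term it would be a second global test over four arms; run within arms it would be another before-after comparison. Neither would supply a contrast.

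**Conclusion.** The omission is real and should be fixed, but it is not fatal, because a valid global randomized test exists. As written, a significant Kruskal-Wallis result would bring no formal inference on which exercise differs and no interval for the difference, and the arm-specific Wilcoxon P values cannot stand in for either.

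The omission itself rests on the text alone. Its size rests on the assumptions stated above and on the one-against-three pattern. At n=10 the advantage of Tukey over the Wilcoxon tests is small if the other arms change by 0.5 SD (45% against 39%) and large at 0.8 SD or more (45% against 7% or less). At n=15 it is large throughout (68% against 20% or less).

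**What to change.** Keep Kruskal-Wallis as the global test and add pairwise between-arm contrasts of VAS change, reported whatever the global result. Two coherent options:

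- All six pairs on mean change, with Tukey-adjusted tests and simultaneous 95% intervals. This fits the planned mean and SD.
- To stay rank-based, Mann-Whitney tests at 0.05/6 = 0.0083 with Hodges-Lehmann differences and 99.17% intervals.

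State that within-arm changes are descriptive and not evidence of a treatment effect.

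The work is a short addition to Statistical Methods and a few lines of analysis, with no added patients. The price is power and width. For 1.30 SD, each Tukey contrast has about 59% power (n=10) or 82% (n=15), with the half-widths shown above; Mann-Whitney at 0.05/6 has about 44% and 72%. A rank-based global test and mean-based contrasts can also disagree, so the report should say how that would be read.

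The Subjects section says "This study was conducted between May of 2016 and April of 2017", and the document is dated April 2017. If the data have already been analysed, label the contrasts post hoc; the differences and intervals still improve the report.

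Two related matters are separate and are not settled here: which VAS reading (rest or activity) and time point is primary, and whether the repeated measures ANOVA has a group factor.
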